9.4 Pharmacodynamic Evaluations

Serum and whole blood samples for the analysis of pharmacodynamic markers will be collected according to the Time and Events Schedule. These samples will be used to better understand the biology of RA, to analyze differences between responders and non-responders, and to assess loss of response. The samples to be collected include whole blood for RNA and serum for the evaluation of inflammation-associated proteins and other analytes such as but not limited to microRNAs.

9.5 Pharmacogenetics (DNA) Evaluations

Assessment of genetic factors such as DNA methylation will be completed. Only DNA research related to sirukumab or to the diseases for which this drug is developed will be performed. Subjects who agree to participate in this optional portion of the study must sign a separate pharmacogenetics informed consent. Further, a subject may withdraw such consent at any time without affecting their participation in other aspects of the study, or their future participation in the study.

9.6 SmartJect™ Autoinjector Usability Substudy

In this substudy, a select number of subjects at selected sites in English-speaking countries who are enrolled in CNTO136ARA3004 will be consented and enrolled in a SmartJect™ AI Usability substudy. Subjects will not be required to participate in the substudy, and can enter the CNTO136ARA3004 LTE study independent of participation in the substudy. Subjects completing the substudy will return to the LTE study for the remainder of their study treatments. Site personnel in the substudy will observe and document 2 scheduled self-administrations of study agent by subjects using the PFS-AI. All substudy subjects will also complete an e-diary regarding their experiences with at-home use of PFS-AI for an additional 12 weeks of study treatment. A subset of these subjects will also have a detailed interview at their final substudy visit regarding their at-home-use experience. For additional details, refer to the PFS-AI Usability Substudy Protocol.

9.7 Health Economics Evaluations

Health economics evaluations on employment status, impact of disease on daily productivity, and time lost from work will be collected. The impact of disease on patients' daily work productivity will be measured using a VAS. The scale ranges from “not at all affected” to “affected very much”.

9.8 Safety Evaluations

Details regarding the DMC and CEC are provided in Sections 11.10 and 11.11, respectively.

As noted in Section 3.2.6, AEs of interest have been identified. These are: hematologic laboratory abnormalities (decreases in neutrophils and platelets), hepatobiliary laboratory abnormalities, lipid parameter abnormalities, serious CV events, infections, malignancies, and gastrointestinal perforations.

The study will include the following evaluations of safety and tolerability according to the time points provided in the Time and Events Schedule:

Adverse Events

Adverse events will be reported by the subject (or, when appropriate, by a caregiver, surrogate, or the subject's legally-acceptable representative) for the duration of the study. Adverse events will be followed by the investigator as specified in Section 12.

Clinical Laboratory Tests

Blood samples for serum chemistry and hematology will be collected. The investigator must review the laboratory report, document this review, and record any clinically relevant changes occurring during the study in the AE section of the CRF. The following tests will be performed by the central laboratory:

- Hematology Panel
 - hemoglobin
 - hematocrit
 - RBC count
 - WBC count with differential
 - platelet count

- Serum Chemistry Panel
 - sodium
 - potassium
 - chloride
 - bicarbonate
 - AST
 - ALT
 - alkaline phosphatase
 - calcium

CNTO 136 (sirukumab): Clinical Protocol CNTO136ARA3004 – Amendment 3

- | | |
|-------------|--|
| - BUN | -phosphate |
| -creatinine | -albumin |
| -glucose | -total protein |
| | -total bilirubin, with fractionation if hyperbilirubinemia |
- Lipid Panel (fasting)

-total cholesterol	-high-density lipoprotein (HDL)
-low-density lipoprotein (LDL)	-triglycerides
 - Urine Pregnancy Testing for women of childbearing potential only.

Additional assays may be performed on lipid panel specimens to further characterize the changes in lipid profile following treatment with sirukumab. Additional laboratory tests may be performed as determined by the Sponsor for the further evaluation of subjects.

Subject Lab Data Access

Subjects at selected sites in the US will be offered the opportunity to consent to join a secure, web-based platform managed by a third party vendor so that they may access results to select clinical laboratory tests collected during the study (as defined above with the exception of RBC count). More details will be provided in the Informed Consent Form for these subjects.

Pathology

If a subject requires tissue sampling for the evaluation of an adverse event, the Sponsor may request that the sample be sent for additional central evaluation.

Vital Signs

Blood pressure and body weight will be measured.

Physical Examination

A general physical examination will be performed as indicated in [Table 1](#). Clinically significant findings should be reported as AEs.

Allergic Reactions

All subjects will be observed carefully for symptoms of allergic reactions for at least 30 minutes after the SC injection of study agent at the study site at least until the study becomes open-label. If mild or moderate allergic reaction is observed, acetaminophen 650 mg PO or NSAIDS and diphenhydramine 25 mg PO or IV may be administered. If the reaction is not severe, subsequent injections at the appropriate treatment intervals may be undertaken with caution. Subjects who self-inject the study agent away from the study site will receive detailed instructions on how to monitor and report AEs.

Subjects with severe reactions following an injection such as bronchospasm with wheezing and/or dyspnea requiring ventilator support, or symptomatic hypotension with a decrease in

systolic blood pressure greater than 40 mm Hg will not be permitted to receive any additional study agent injections. In the case of such reactions, appropriate medical treatment should be administered.

Injection Site Reactions

An injection site reaction is any unfavorable or unintended sign that occurs at the study agent injection site. All subjects must be carefully observed for symptoms of an injection site reaction. Subjects will be observed for at least 30 minutes after the SC injection of study agent for symptoms of an injection-site reaction at least until the study becomes open-label. If an injection site reaction is observed, the subject should be treated at the investigator's discretion. Any adverse reaction (eg, pain, erythema, and/or induration) should be noted on the AE page of the eCRF.

Early Detection of Active Tuberculosis

To aid in the early detection of TB reactivation or new TB infection during study participation, subjects must be evaluated for signs and symptoms of active TB at scheduled visits (refer to the Time and Events Schedule). The following series of questions is suggested for use during the evaluation:

- “Have you had a new cough of > 14 days’ duration or a change in a chronic cough?”
- “Have you had any of the following symptoms:
 - Persistent fever?
 - Unintentional weight loss?
 - Night sweats?”
- “Have you had close contact with an individual with active TB?” (If there is uncertainty as to whether a contact should be considered “close,” a physician specializing in TB should be consulted.)

If the evaluation raises suspicion that a subject may have TB reactivation or new TB infection, study agent administration should be interrupted and an immediate and thorough investigation should be undertaken, including, where possible, consultation with a physician specializing in TB.

Investigators should be aware that TB reactivation in immunocompromised subjects may present as disseminated disease or with extrapulmonary features. Subjects with evidence of active TB must immediately discontinue study agent and should be referred for appropriate treatment.

Subjects who experience close contact with an individual with active TB during the conduct of the study must have a repeat chest radiograph, a repeat QuantiFERON TB Gold test ([Appendix A](#)), a repeat tuberculin skin test ([Appendix B](#)) in countries in which the QuantiFERON-TB Gold test is not approved/registered, and, if possible, referral to a physician specializing in TB to determine the subject's risk of developing active TB and whether treatment for latent TB is warranted. Study agent administration should be interrupted during the

investigation. A positive QuantiFERON-TB Gold (or tuberculin skin) test result should be considered detection of latent TB. Appropriate treatment for latent TB is defined according to local country guidelines for immunocompromised patients. If no local country guidelines for immunocompromised patients exist, US guidelines must be followed or the subject must be excluded from the study. If recommended, treatment for latent TB must be initiated prior to or simultaneously with the administration of further study agent. Subjects who discontinue treatment for latent TB prematurely or who are noncompliant with therapy must immediately discontinue further administration of study agent and should return for all subsequent scheduled study visits (see Section 10.2). A subject whose first QuantiFERON-TB Gold test result is indeterminate should have the test repeated. In the event that the second QuantiFERON-TB Gold test result is also indeterminate, the subject should be excluded from the study.

Hepatitis B Monitoring

Subjects who are HBsAg- /HBcAb+ only, without detectable HBV DNA, should be monitored according to local guidelines. If local guidelines do not exist for HBV monitoring in these types of patients, monitoring should be performed following consultation with a hepatitis B specialist.

HBsAg- /HBsAb+ subjects who are HBcAb- or +, and without detectable HBV DNA, should be monitored if recommended under local guidelines related to HBV and biologic anti-rheumatic agents.

Hepatobiliary abnormalities

In the event of hepatobiliary abnormalities such as AST or ALT ≥ 3 times ULN, confirmatory testing should be repeated using a liver chemistry kit and clinical assessment for symptoms of hepatic dysfunction done as soon as possible. A liver chemistry kit will include the following tests: ALT, AST, alkaline phosphatase, total and direct bilirubin. If the hepatobiliary laboratory abnormality is confirmed, then a thorough evaluation should be performed, including the following, as appropriate:

- Medical and family history
- Review of medications, alcohol, and other substance use
- Physical examination (including vital signs, examination of liver and abdomen, other stigmata of hepatic disease)
- Abdominal ultrasound with consideration of further imaging (eg, CT, MRI, MRCP, ERCP, Doppler studies of hepatic vessels, etc., if indicated based on ultrasound findings or clinical situation)
- Laboratory evaluation using a hepatobiliary abnormalities kit: Complete blood counts with eosinophil count, international normalized ratio (INR), viral hepatitis serology testing (anti-Hepatitis A virus (HAV) IgM, HBsAg, anti-HBs, anti-HB core total, anti-HB core IgM, anti-HCV, HCV RNA, anti-Hepatitis E virus IgM, Epstein-Barr virus IgM and Cytomegalovirus IgM), total protein and globulins, antinuclear antibody, anti-smooth muscle antibody, iron markers (iron, TIBC, ferritin)

CNTO 136 (sirukumab): Clinical Protocol CNTO136ARA3004 – Amendment 3

Consultation with a specialist may be warranted. See Section 10.2 for specific instructions regarding discontinuation of treatment guidelines and evaluation of hepatobiliary abnormalities. Temporary or permanent discontinuation of study agent may be required (see Section 10.2). Temporary discontinuation or dose adjustment of MTX may be required (see Section 8.1.2).

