4.1 Inclusion Criteria

Each potential subject must satisfy all of the following criteria to be enrolled in the study. Each subject must:

CNTO 136 (sirukumab): Clinical Protocol CNTO136ARA3004 – Amendment 3

1. Have completed the final study agent administrations in the primary study (Week 104 injection in CNTO136ARA3002 or Week 52 injection in CNTO136ARA3003) including all other assessments required for these visits. The subject will then be deemed to have completed participation in those studies and will be eligible to enroll in this long-term extension study.
2. Sign an informed consent form (ICF) indicating that they understand the purpose of and procedures required for the study and are willing to participate in the study.
3. Sign an informed consent form (ICF) for pharmacogenetics research in order to participate in the optional pharmacogenetics component of this study, where local regulations permit. Refusal to give consent for this component does not exclude a subject from participation in this clinical study.

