10.2 Discontinuation of Treatment

If a subject's study treatment must be discontinued before the end of the treatment regimen, this will not result in automatic withdrawal of the subject from the study.

Study agent administration to a subject must be permanently discontinued if any of the following occur:

1. The investigator (in consultation with the medical monitor) believes that for safety reasons (eg, adverse event) it is in the best interest of the subject to stop treatment.
2. Anaphylactic reaction resulting in bronchospasm with wheezing, or dyspnea requiring ventilatory support, or symptomatic hypotension with a greater than 40 mm Hg decrease in systolic blood pressure that occurs following a study agent administration.
3. Reaction suggestive of serum sickness occurring 1 to 14 days after study agent injection. These may be manifested by symptoms of myalgias, arthralgias, fever, rash, pruritus, facial, hand, or lip edema, dysphagia, urticaria, sore throat, and/or headache.
4. Opportunistic infection, ie, an infection by an organism that usually causes disease only in a host whose resistance is lowered (eg, *Pneumocystis jirovecii*, coccidioidomycosis, *Mycobacterium avium*).
5. TB
 - a. Active TB
 - b. Subject with latent TB who discontinues treatment for latent TB prematurely or is not compliant with treatment for latent TB
6. Malignancy, excluding nonmelanoma skin cancer.

CNTO 136 (sirukumab): Clinical Protocol CNTO136ARA3004 – Amendment 3

7. Demyelination, either central or peripheral.
8. Pregnancy during study participation.
9. Drug induced liver injury, including any one of the following:
 - a. Alanine transferase (ALT) or aspartate transferase (AST) $\geq 5 \times$ ULN but $< 8 \times$ ULN and cannot be monitored weekly for ≥ 2 weeks.
 - b. ALT or AST $\geq 8 \times$ upper limit of normal (ULN)
 - c. ALT or AST $\geq 5 \times$ ULN for 2 or more weeks
 - d. ALT or AST $\geq 3 \times$ ULN and total bilirubin $\geq 2 \times$ ULN (upper limit of normal) ($> 35\%$ direct bilirubin) (or ALT or AST $\geq 3 \times$ ULN **and** INR > 1.5 , if INR measured).

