 - Serum acetaminophen adduct HPLC assay (quantifies potential acetaminophen contribution to liver injury in subjects with definite or likely acetaminophen use in the preceding week)
 - Consider serum ethanol as clinically appropriate.
 - Liver ultrasound with consideration of further imaging (eg, CT, MRI, MRCP, ERCP, Doppler studies of hepatic vessels, etc., if indicated based on ultrasound findings or clinical situation)
10. Two confirmed consecutive absolute neutrophil counts of $< 0.5 \times 10^3/\mu\text{L}$ (SI: $< 0.5 \times 10^9$ cells/L).
 11. Two confirmed consecutive platelet counts $< 50,000/\mu\text{L}$ (SI: $< 50 \times 10^9$ cells/L).
 12. QTc > 500 msec* or uncorrected QT > 600 msec, Change from baseline: QTc > 60 msec*
*based on average QTc value of triplicate ECGs
 13. The initiation of protocol-prohibited medications. (see Section 8.2).
 14. Acute diverticulitis requiring antibiotic treatment
 15. Gastrointestinal perforation
 16. If sirukumab becomes approved in the subject's country of residence, it may no longer be offered by the Sponsor in CNTO136ARA3004. In this case, study agent administrations will be discontinued after 52 weeks of treatment for subjects who enrolled after completing participation in study CNTO136ARA3002, and after 104 weeks of treatment for subjects who enrolled after completing participation in CNTO136ARA3003. At that point the subject will have the opportunity to discuss treatment options with their treating physician.

CNTO 136 (sirukumab): Clinical Protocol CNTO136ARA3004 – Amendment 3

Subjects should not receive study agent administrations during the course of a serious infection. Discontinuation of study agent administration must be strongly considered for subjects who develop a serious infection such as sepsis or meningoenephalitis, and also should be considered for subjects who have serious infections requiring hospitalization or IV antibiotic therapy. Discontinuation of study agent administration should also be considered for severe injection-site reactions.

Subjects who discontinued study agent administration should continue participating in the study for safety and efficacy follow-up (Table 2).

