10.3 Withdrawal from the Study

A subject will be withdrawn from the study for any of the following reasons:

- Lost to follow-up
- Withdrawal of consent
- Death

If a subject discontinues study agent administration before the end of the study, follow-up assessments should be obtained as per the Time and Events Schedule described in [Table 2](#).

If a subject is lost to follow-up, every reasonable effort must be made by the study site personnel to contact the subject and determine the reason for discontinuation/withdrawal. The measures taken to follow up must be documented.

When a subject withdraws before completing the study, the reason for withdrawal is to be documented in the CRF and in the source document. Study agent assigned to the withdrawn subject may not be assigned to another subject. Subjects who withdraw will not be replaced.

Withdrawal from Pharmacodynamic Research

The subject may withdraw consent for pharmacodynamics research while remaining in the clinical study. In such a case, any stored samples will be destroyed upon communication from the site to the Sponsor. No pharmacogenetics testing will be conducted on these samples. This does not include those samples specifically collected for pharmacogenetic analysis for which separate optional consent was obtained.

Withdrawal from Pharmacogenetics Research

The subject may withdraw consent for pharmacogenetics research while remaining in the clinical study. In such a case, any DNA extracted from the subject's blood will be destroyed upon communication from the site to the Sponsor. If requested, the investigator will receive written confirmation from the Sponsor that the sample has been destroyed.

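### Protocol Section 9.8 tells sites to exclude enrolled, TB-exposed subjects from the study; this conflicts with Sections 10.2 and 10.3 and, read literally, ends their scheduled safety follow-up

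*Protocol*

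**What the plan says.** The passage is in Protocol Section 9.8, under early detection of active tuberculosis. It applies to people already enrolled: "Subjects who experience close contact with an individual with active TB during the conduct of the study must have a repeat chest radiograph", together with a repeat QuantiFERON-TB Gold test (and a tuberculin skin test where QuantiFERON is not approved). Study agent is interrupted while this is investigated. Two sentences then remove the subject:

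- On a repeated unclear test: "In the event that the second QuantiFERON-TB Gold test result is also indeterminate, the subject should be excluded from the study".
- On treatment of latent TB where a country has no guidelines for immunocompromised patients: "US guidelines must be followed or the subject must be excluded from the study".

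Other sections point the other way. When treatment stops early, Section 10.2 says "this will not result in automatic withdrawal of the subject from the study", and it ends with "Subjects who discontinued study agent administration should continue participating in the study for safety and efficacy follow-up", citing Table 2. Section 10.3 opens its list with "A subject will be withdrawn from the study for any of the following reasons" and names loss to follow-up, withdrawal of consent and death.

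**The concern.** The wording suits a screening section, but these subjects are on treatment. A site following Section 9.8 to the letter would take a subject out of the study for a reason that the withdrawal section does not contain. It would do so when that subject has a known TB exposure and an unresolved test.

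The primary endpoint counts subjects with long-term safety events, including serious infections, through the end of the study, and active TB is an adverse event of special interest (Section 12.4). Section 3.2.3 justifies the 16-week follow-up as covering at least five half-lives of sirukumab. If subjects leave scheduled observation because of TB exposure, the reason for leaving is linked to the outcome being counted. Section 11.2 plans no imputation, so an event missed in this way is simply absent from the count.

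**Working it through.** No arithmetic applies. The protocol states no figure on this point, and the number of subjects affected cannot be estimated because neither a TB-contact rate nor an indeterminate-test rate is given. The check sets the passages side by side.

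**1. Could this be an entry rule?** No. Entry rests on finishing the parent study (Section 4.1: "Have completed the final study agent administrations in the primary study") and on consent. Neither Section 4.1 nor Section 4.2 contains a TB test, and the Section 9.8 paragraph concerns contacts that arise on study.

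**2. How do the other sections treat the same situations?**

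| Place | Second indeterminate test | No local guidelines, US guidelines not followed |
|---|---|---|
| Section 9.8 | Exclude from study | Exclude from study |
| Section 10.2, 16 criteria | Not listed; the TB item covers active TB and stopped or non-compliant latent-TB treatment | Not listed as such |
| Section 10.3, 3 reasons | Not listed | Not listed |
| Appendix A | Repeat an indeterminate test; no exclusion mentioned | Follow US guidelines; no exclusion mentioned |
| Appendix B | Not addressed | Follow US guidelines; no exclusion mentioned |

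A second indeterminate test therefore appears in 0 of 16 discontinuation criteria and 0 of 3 withdrawal reasons.

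**3. What would exclusion do to follow-up?** Section 9.1.4 and Table 2 footnote a both give the 16-week follow-up to subjects who stop injections but do not terminate participation. A subject excluded from the study, in the ordinary sense, fails that condition. Table 2 has four visits (Weeks 4, 8, 12 and 16 after the last injection), with adverse events reviewed at each and laboratory panels at Weeks 8 and 16. Those visits are what a literal reading would lose.

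**4. What would remain?** Under Section 12.3.1, serious adverse events reported spontaneously within 4 months of the last dose must still be reported. Under Section 12.3.2, a death in that period counts as serious, and serious events unresolved when participation ends are still followed. Routine adverse-event collection, by contrast, ends at the subject's last study visit. The change is from scheduled inquiry to spontaneous reporting.

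**5. Can a site disregard the sentence?** Section 3.1 allows no waivers except for immediate safety concerns, so the text gives no general permission to do so.

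**The case against.** The best reply is that the word 'excluded' is loose and means only that study agent stops. Section 9.8 never says that follow-up ends. Section 10.3 itself adds that subjects who stop study agent early should have the Table 2 assessments, with no condition about terminating participation, and it does not state that its three reasons are exhaustive. This stands in part: the loss of follow-up is inferred from the literal wording and is not stated outright. It does not remove the conflict, because Section 9.8 speaks of the study and not of study agent, and Section 9.1.4 and Table 2 do carry the condition.

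Three stronger readings are tempting, and the documents do not support them.

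- A reader might infer a second contradiction from the sentence in the same paragraph that sends subjects who abandon latent-TB treatment back for their remaining visits, taking these to be Table 1 visits. That sentence cites Section 10.2, which leads to Table 2, and Table 1 footnote a also sends subjects who stop injections to Table 2. The visits meant are most naturally the Table 2 visits.
- A reader might infer that sites have no rule at all for study agent. Section 9.8 requires interruption during the investigation, and Section 10.2 item 1 requires permanent discontinuation when the investigator, consulting the medical monitor, judges that safety calls for it. What is missing is a specific criterion for a second indeterminate result.
- A reader might infer that all safety collection stops for these subjects. Step 4 of the check shows that it does not.

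**Conclusion.** The inconsistency is real and stands in the current protocol text. Section 9.8 twice prescribes removal from the study for enrolled subjects, on grounds that Section 10.3 does not list, against the approach of Section 10.2, and without support in Appendix A or B. On a literal reading the cost per affected subject is the four scheduled follow-up visits over 16 weeks.

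The consequence is best described as possible selective under-ascertainment of serious infections and active TB. The endpoint is a descriptive count with no hypothesis test, so no error rate or power is affected. Few subjects are probably involved, but that is a judgement. The conclusion assumes that sites give 'excluded' its ordinary meaning; if the sponsor intends it to mean stopping study agent only, the follow-up survives and the defect is one of wording. Either way it is worth correcting, because safety is the primary objective and the text leaves the answer open.

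**What to change.** Reconcile Section 9.8 with Sections 9.1.4, 10.2 and 10.3, Table 2, and Appendices A and B:

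- State, for both sentences in Section 9.8, whether exclusion means stopping study agent or leaving the study.
- Word the result so that a TB test result or a guideline issue does not by itself end scheduled safety observation, and name the visit schedule that applies.
- Make the handling of study agent after a second indeterminate result explicit and consistent between Sections 9.8 and 10.2. The content of that rule is for the sponsor's medical team; this review takes no position on it.

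The cost is a few words in an amendment. The added burden is scheduled safety visits for what is likely to be a handful of subjects, and where the Table 2 schedule applies, its four visits are already defined.
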